10.2.3. Recording and Following Up SAEs

SAE Recording

- Care will be taken not to introduce bias when detecting SAEs. Open-ended and non-leading verbal questioning of the participant is the preferred method to inquire about occurrences.
- When an SAE occurs, it is the responsibility of the investigator to review all documentation (eg, hospital progress notes, laboratory reports, and diagnostics reports) related to the event.
- The investigator will then record all relevant SAE information in the eCRF.
- After the initial SAE report, the investigator is required to proactively follow each participant at subsequent visits/contacts. All SAEs will be followed until resolution, stabilization, the event is otherwise explained, or the participant is lost to follow-up.
- It is **not** acceptable for the investigator to send photocopies of the participant's medical records to the sponsor in lieu of completion of the SAE eCRF page.
- There may be instances when copies of medical records for certain cases are requested by the Medical Monitor, the IDMC or the sponsor. In this case, all participant identifiers, with the exception of the participant number, will be redacted on the copies of the medical records before submission.

- The investigator will attempt to establish a diagnosis of the event based on signs, symptoms, and/or other clinical information. Whenever possible, the diagnosis (not the individual signs/symptoms) will be documented as the SAE.
- SAEs will be assessed for intensity and causal relationship to the study intervention.

SAE Follow-up and Resolution

The investigator is obligated to perform or arrange for the conduct of supplemental measurements and/or evaluations as medically indicated to elucidate the nature and/or causality of the SAE as fully as possible. This may include additional laboratory tests or investigations, histopathological examinations, or consultation with other health care professionals.

If a participant dies during participation in the study or during a recognized follow-up period, the investigator will provide the sponsor with a copy of any post-mortem findings including histopathology, if available.

New or updated information will be recorded in the originally completed eCRF.

The investigator will submit any updated SAE data to the sponsor within 24 hours of receipt of the information.

The onset and resolution dates of the event and medical care taken in response to the event will be documented.

SAEs will be considered resolved when the condition returns to normal or returns to the participant's baseline status as established on Study Day 1, or when the condition has stabilized with the expectation that it will remain chronic.

If the event has not resolved by the final study visit, it will be documented as "ongoing" on the eCRF, however, follow-up of the SAE must continue until resolved or the condition has stabilized. Information recorded on the eCRF must be substantiated in the source documents.

The resolution date to be recorded on the eCRF is the last date on which the participant experienced the SAE.

Assessment of Intensity

The investigator will make an assessment of intensity for each SAE reported during the study and assign it to 1 of the following categories:

- Grade 1, Mild: An event that is easily tolerated by the participant, causing minimal discomfort and not interfering with everyday activities.
- Grade 2, Moderate: An event that causes sufficient discomfort and interferes with normal everyday activities.
- Grade 3, Severe: An event that prevents normal everyday activities. An AE that is assessed as severe should not be confused with a SAE. Severe is a category utilized for rating the intensity of an event; and both AEs and SAEs can be assessed as severe.
- Grade 4 Potentially life-threatening symptoms, causing inability to perform basic selfcare functions with intervention indicated to prevent permanent impairment, persistent disability, or death.

An event is defined as 'serious' when it meets at least 1 of the predefined outcomes as described in the definition of an SAE, NOT when it is rated as severe.

Assessment of Causality

The investigator is obligated to assess the relationship between study intervention and each occurrence of each SAE. The investigator will assess whether the SAE is either:

Related: An SAE is considered related to study intervention if there is a reasonable possibility that the study intervention contributed to the SAE. *or*

Not related: There is no reasonable possibility that the SAE is causally related to administration of the study intervention. There are other more likely causes for the SAE.

The investigator will use clinical judgment to determine the relationship.

Alternative causes, such as underlying disease(s), concomitant therapy, and other risk factors, as well as the temporal relationship of the event to study intervention administration will be considered and investigated.

For each SAE, the investigator must document in the medical notes that he/she has reviewed the SAE and has provided an assessment of causality. There may be situations in which an SAE has occurred and the investigator has minimal information to assess causality to include in the initial report. However, it is very important that the investigator always provide an assessment of causality with the initial submission of the SAE data.

The investigator may change his/her assessment of causality when considering additional follow-up information and submit an SAE follow-up report with the updated causality assessment. The causality assessment is one of the criteria used when determining regulatory reporting requirements.

Assessment of Outcome

The outcome of each SAE must be reported to the sponsor. For analysis purposes, the outcome for serious adverse events will be determined on the final study visit.

Outcome of all SAEs will be classified as one of the following:

•Resolved

•Resolved with sequelae

•Ongoing

•Death.

10.2.4. Reporting SAEs

SAE Reporting to CRO via an Electronic Data Collection Tool

- The primary mechanism for reporting an SAE to the CRO will be the electronic data collection tool.
- If the electronic system is unavailable, then the site will use the paper SAE data collection tool (see next section) in order to report the event within 24 hours.
- The site will enter the SAE data into the electronic system as soon as it becomes available.
- After the study is completed at a given site, the electronic data collection tool will be taken off-line to prevent the entry of new data or changes to existing data.
- If a site receives a report of a new SAE from a study participant or receives updated data on a previously reported SAE after the electronic data collection tool has been taken off-line, then the site can report this information on a paper SAE form (see next section) or to the Medical Monitor by telephone.
- Contacts for SAE reporting can be found in the Study Manual.

SAE Reporting to CRO via Paper Case Report Form

- Email transmission of the SAE paper CRF is the preferred method to transmit this information.
- In rare circumstances and in the absence of email, notification by telephone is acceptable with a copy of the SAE data collection tool sent by overnight mail or courier service.
- Initial notification via telephone does not replace the need for the investigator to complete and sign the SAE CRF pages within the designated reporting time frames.
- Contacts for SAE reporting can be found in the Study Manual.

11. References

10.1002/14651858.CD005496.pub4. Update in: Cochrane Database Syst Rev. 2020 Oct 15;10:CD005496. PMID: 24723255.

The primary purpose of this protocol update was to combine the enrollment activities with the Day 1 (randomization) visit and clarify other study procedures. The major changes incorporated into this protocol (Version 3.0) relative to the prior approved version (Version 2.0) are summarized below. Editorial and formatting changes are not included in this summary.

| Section # and Name | Description of Change | Brief Rationale |
|-----------------------------------------------------------------------------------------------------------------|-----------------------------------------------------------------------------------------------------------------------------------------------------------------------------------------------------------------------------------------------------------------------------|--------------------------------------------------------------------------------------------------------------------------------------------------------------------------------------------------------|
| Page 3 | Added Principal Investigator signatory page. | To have signature recorded together with other study documents in a single location |
| Throughout the document | Removed the word "unsolicited" before 'AEs'. | This study does not include solicited AEs, so all AEs are unsolicited. However, to avoid any confusion, the word "unsolicited" was removed to clarify that all AEs will be recorded. |
| Synopsis, Objectives and Endpoints (Table 1) and Section 9.7 Table 5 Secondary Estimands | Updated text in Table 1 and Table 5 to align wording across the tables. | For clarification |
| Synopsis, Schedule of Activities (SOA Table 2) and Main Study Schema (Figure 1), and Section 4.1 | Combined enrollment activities with the Day 1 (randomization) visit. Added text to indicate that screening may occur on Day 1 with enrollment and randomization, or separately within the protocol-specified window. | To clarify the timing of screening, enrollment, and randomization activities |
| Synopsis, SoA (Table 2) | Updated procedural details to align throughout the protocol. Updates include separating medication collection for the infant and the infant's mother, specifying time points for provision and collection of diaries, and addition of explanatory footnotes. | For clarification |
| Section 4.4 End of Study Definition | Clarified the definition of study completion for an individual participant. | For clarification |

| Section # and Name | Description of Change | Brief Rationale |
|-----------------------------------------------------------------------------------------------------------------------|-------------------------------------------------------------------------------------------------------------------------------------------------------------------------------------------------|----------------------------------------------------------------------------------------------------------------------------------------|
| Section 5.3 Screen Failures and Section 10.1.3 Informed Consent Process | Replaced text that stated 'rescreening will not be allowed', to allow for rescreening if screening visit is outside of the 7-day planned window, due to a delay in hospital discharge. | For flexibility during the screening process |
| Section 5.1 Inclusion criteria | Specified that enrollment is on Day 1. | To clarify when the participant is enrolled in the study |
| Section 5.1and 5.2, Inclusion/exclusion criteria, Section 6 Study intervention and throughout document | Replaced "mother" with "participant's parent/legal guardian" unless only the mother can perform a particular task. | To allow more flexibility at participant's home so that another parent or legal guardian may perform some study activities |
| Section 6.2Measures to Minimize Bias: Randomization and Blinding | Clarified individuals who will be blinded and unblinded. | For clarification |
| Section 6.3 Study Intervention Compliance | Removed confirmation of refrigeration temperature using a temperature logger. | Temperature data loggers will not be used to monitor the study intervention. |
| Section 6.4 Feeding history | Added details to be recorded, including whether the full dose was taken, and whether a repeat dose was administered. | For clarification |
| Section 7.1 Discontinuation | Added details regarding investigator decision to stop the study intervention for an individual participant. | For clarification |
| Section 7.3 Replacement of Participants | Added new section "Replacement of Participants" and a statement that participants will not be replaced. | To specify that participants will not be replaced if early discontinuation from study occurs |
| Section 8.1 Demographic and Baseline Characteristics | Reworded text and added details regarding what will be collected at screening and at Day 1. | For clarification |
| Section 8.3.3 Vital Signs | Replaced respiratory rate with pulse oximetry | For clarification |

| Section # and Name | Description of Change | Brief Rationale |
|-----------------------------------------------------------------------------------------------------------|------------------------------------------------------------------------------------------------------------------------------------------------------|------------------------------------------------------------------------------------------------------------------------------------------------------|
| Section 8.4.5 Independent Data Monitoring Committee (IDMC) | Added further details about possible IDMC recommendations and about sponsor decision to terminate the study for safety reasons. | For clarification |
| Section 10.1.11 Financial Disclosure | Added this new section. | For clarification |
| Section 10.1.3 Informed Consent Process | Included a statement that the participant's mother will also sign the Informed Consent Form to allow collection of her medical information. | For clarification |
| Protocol Version History and Summary of Changes page 4, and Section 12 Protocol Amendments | Moved text from page 3 to newly created Section 12, Protocol Amendments. | To move details from previous amendment changes to end of document and provide new amendment changes at the beginning of the document |

Minor editorial changes were made throughout the protocol for corrections or to clarify text.

Overall Rationale for changes in Version 2.0:

The protocol was amended to include a sub-study to monitor the temperatures of the refrigerators used in the main study. The aim of this optional, prospective, observational sub-study is to collect information on reliability of refrigeration in the geographic areas where the study is being conducted and where *B. infantis* supplementation may be recommended by WHO, if supported by clinical data. As of 2020, 733 million people did not have access to electricity, and over 75% of people living in sub-Saharan Africa did not have access. In order to get a geographical cross-representation in this sub-study, each clinical site will be asked to enroll up to 20% of their overall study population into the sub-study.

| Section # and Name | Description of Change | Brief Rationale |
|----------------------------------------------------------------------------------------|------------------------------------------------------------------------------------------------------------------------------------------------------------------------------------------|------------------------------------------------------------------------------------------------------------------------------------------------|
| 1.1 Synopsis 4.4 Optional Sub-Study and Table 2 Schedule of Activities. | This section was added to the protocol to specify use of a temperature data logger over a 2- week period in the home refrigerators of a subset of the study participants. | To collect information on reliability of refrigeration in the geographic areas where the study is being conducted. |
| Minor changes | were made throughout the protocol inclu | iding the following: |
| Throughout protocol | The term 'formula' was replaced with 'water' for product reconstitution. | To specify that water can be used to mix with the Bi-26 or placebo, instead of formula, if breastmilk is not available for a given dose. |
| Section 2.1 Background | Text added to clarify GRAS status information. | To provide additional information on the GRAS designation |
| Section 2.2. Risk Benefit Assessment | New data from the SYNERGIE study added. | To provide evidence to support the potential for positive clinical outcomes with B. infantis supplementation. |
| | | |
| Section 8.6 Biomarkers | Blood volume changed from 2 mL to 4mL. | To allow for adequate blood volume for testing. |

Minor editorial changes were made throughout the protocol for corrections or to clarify text.

Signature Page for: Gates MRI-MNK01-301 Protocol Version 4.0 (12 Sep 2022)

Gateway RIM Document #: MNK01-CLIN-000003 v4.0

| Document Approvals | | | | |
|---------------------|---------------------------------------------------------------|--|--|--|
| eSignature Approval | Clinical Development 13-Sep-2022 20:40:53 GMT+0000 | | | |
| eSignature Approval | Biometrics & Data Management 14-Sep-2022 13:15:44 GMT+0000 | | | |
| eSignature Approval | Chief Medical Officer 14-Sep-2022 13:37:30 GMT+0000 | | | |

2 DOCUMENT HISTORY

Document	Date
Original SAP version 1	18 August 2023

Confidential Page 5 of 50

4 LIST OF ABBREVIATIONS AND DEFINITIONS OF TERMS

ACR Assessment/collection/result

ATC Anatomical Therapeutic Chemical

AE Adverse event

Bi-26 Strain of Bifidobacterium longum, B. infantis

CFB Change from baseline

CHAIN The Childhood Acute Illness and Nutrition Network

CI Confidence interval
CRF Case report form

CRP Complete Randomization Probability

DACP Dynamic Allocation with Complete Randomization

DHS Demographic and Health Survey

eCRF Electronic case report form

EC Ethics committee

EDC Electronic data capture

EoS End of study

GA Gestational age

HIV Human immunodeficiency virus

ICF Informed consent form

IDMC Independent Data Monitoring Committee

IFDC Infant feeding diary card

ITT Intent-to-treat

MedDRA Medical Dictionary for Regulatory Activities

mITT Modified Intention-to-treat

MMRM Mixed model for repeated measures

MUAC Mid-upper arm circumference
PCI Potentially clinically important

PE Physical examinations

PP Per Protocol
PT Preferred term

RTSM Randomization and Trial Supply Management

Confidential Page 8 of 50

SAE	Serious adverse event
SAP	Statistical analysis plan

SAS® Statistical Analysis Software

SD Standard deviation

SES Socioeconomic status
SoA Schedule of Activities
SOC System organ class

TE Temperature excursion

TEAE Treatment emergent adverse event

TLF Table, listing and figure
WAZ Weight-for-age Z-score
WHO World Health Organization
WLZ Weight-for-length Z-score

Confidential Page 9 of 50

5 INTRODUCTION

The purpose of this SAP is to describe the framework for the reporting, summarization, and statistical analysis methodology of the safety and efficacy parameters measured throughout the study. It is based on Protocol Gates MRI-MNK01-301 dated 12 September 2022 (Version 4).

Confidential Page 10 of 50

6 STUDY OBJECTIVES AND ENDPOINTS

6.1 Primary Objective

Table 1. Primary objective

Objective		Estimand	
To evaluate the change in weight (standardized for age) of infants	a)	Population : The Modified Intent to Treat (mITT) population will be used for the analysis.	
receiving Bi-26	b)	Endpoint : Weight-for-age z-score (WAZ) change from baseline (CFB) (Day 1) to the Day 56 visit in Bi-26 group.	
	c)	Population level summary : Mean change from baseline in WAZ in the Bi-26 group compared to placebo with stratification blocking factors and feeding regimen covariate(s).	
	d)	Intercurrent event(s) : Including but not limited to treatment discontinuation.	

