9.7. Primary and Secondary Estimands

Participants randomized to the group receiving 28 days of Bi-26 will be compared to participants randomized to 28 days of placebo for the primary analysis.

Following International Council for Harmonization of Technical Requirements for Pharmaceuticals for Human Use (ICH) E9 (R1) addendum, the estimands relating to the study objectives are constructed by using the 5 following attributes:

- (a) treatment
- (b) population
- (c) variable/endpoint
- (d) population level summary
- (e) intercurrent events.

These attributes were specified to translate the study objective(s) into a treatment effect that is to be estimated (estimand). Refer to Table 4 and Table 5 for a summary of the primary and secondary estimands, respectively.

| Objective | Primary Estimand |
|---------------------------|-------------------------------------------------------------------------------------------------------------------------------------------------------------------------------------|
| To evaluate the change in | a. Population : The mITT population will be used for the analysis. |
| age) of infants receiving | b. Endpoint : WAZ change from baseline (Day 1) to the Day 56 visit in Bi-26 group. |
| B1-20 | c. Population level summary : Mean change from baseline in WAZ in the Bi-26 group compared to placebo with stratification blocking factors and feeding regimen covariate(s). |
| | d. Intercurrent event(s) : Including but not limited to treatment discontinuation. Further details will be specified in the SAP . |

Table 4: Primary Estimands

| Objective | Secondary Estimand | | | | |
|--------------------------------------------------|-------------------------------------------------------------------------------------------------------------------------------------------------------------------------------------------------------|--|--|--|--|
| To evaluate the change in | a. Population : The mITT population will be used for this analysis. | | | | |
| weight of infants receiving Bi-26 | b. Endpoint : weight change (in grams) from baseline (Day 1) to the Day 56 visit in Bi-26 group. | | | | |
| | c. Population level summary : Mean change from baseline in weight in the Bi-26 group compared to placebo with stratification blocking factors and feeding regimen covariate(s). | | | | |
| | d. Intercurrent event(s): Including but not limited to treatment discontinuation. Details will be provided in the SAP. | | | | |

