6.2 Secondary Objectives

Table 2. Secondary Objectives

Objective		Estimand
Key Secondary		
To evaluate the change in weight of	a)	Population : The mITT population will be used for this analysis.
infants receiving Bi-26	b)	Endpoint : weight change (in grams) from baseline (Day 1) to the Day 56 visit in Bi-26 group.
	c)	Population level summary : Mean change from baseline in weight in the Bi-26 group compared to placebo with stratification blocking factors and feeding regimen covariate(s).
	d)	Intercurrent event(s): Including but not limited to treatment discontinuation.
Secondary		
To estimate the treatment response over time associated with Bi-26	a) b)	Population : The mITT population will be used for the analysis. Endpoint : WAZ change from baseline (Day 1) over time through the Day 90 visit (longitudinal assessment) by duration of dosing.
	c)	Population level summary : Mean change from baseline in WAZ over time in the Bi-26 group compared to placebo with stratification blocking factors and feeding regimen covariate(s).
	d)	Intercurrent event(s): Including but not limited to treatment discontinuation.
To assess the proportion of infants	a)	Population : The Safety population will be used for the analysis.
who achieve a specified change in WAZ from baseline to Day 56	re a specified change in b)	Endpoint : Proportion of infants with $a \ge 0.3$, 0.4, and 0.5 change in WAZ from baseline (Day 1) to Day 56 visit.
	c)	Population level summary : Frequency and percentages of infants with a ≥ 0.3 , 0.4, and 0.5 change in WAZ from baseline (Day 1) to Day 56 in the Bi-26 and placebo groups.
	d)	Intercurrent event(s): Including but not limited to treatment discontinuation.

Confidential Page 11 of 50

To assess the proportion of infants who achieve a specified WAZ at Day 56

- a) **Population**: The Safety population will be used for the analysis.
- b) **Endpoint:** Proportion of infants with a WAZ > -2 at Day 56 visit.
- c) **Population level summary:** Frequency and percentages of infants with a WAZ > -2 at Day 56 in the Bi-26 and the placebo groups.
- d) **Intercurrent event(s)**: Including but not limited to treatment discontinuation.

To assess the re-hospitalization rate

- a) **Population**: The Safety population will be used for the analysis.
- b) **Endpoint:** Number of re-hospitalizations for acute non-surgical illness through the Day 56 visit.

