11.2 Demographics and Baseline Characteristics

Demographics and baseline characteristics will be summarized using descriptive statistics by treatment group and overall. The denominators for percentages will be the number of participants in each treatment group with non-missing data for the variable of interest for the ITT population. The number of participants with missing data at baseline, without percentages, will be displayed for each of the variables. Two participant listings will be presented with treatment group, one for demographic variables and the other for baseline variables as listed below, for the ITT population.

The following demographic and baseline variables will be summarized and listed:

- Country (Bangladesh, Kenya, Pakistan, Tanzania).
- Age (days) at enrollment both numeric and categorical (30-59 days, 60-120 days).
- Sex (Male, Female).
- Race (Asian, Black, Indian, White, Other).
- Ethnicity (Bantu, Bengali, Cushite, Kalenjin, Kikuyu, Luo, Luyha, Nilo-Hamite, Pashtun, Punjabi, Sairiki, San, Sindhi, Other).
- Infant been exposed to HIV (Human immunodeficiency virus) (Yes, No).
- Type of HIV exposure (Hospital, Household, Infected Mother, Other, Unknown).
- Infant HIV status, only positive will be indicated as it will be recorded in the medical history.
- Weight (grams).
- Length (cm).
- Mid-upper arm circumference (MUAC).
- Head circumference (cm).
- Skinfold thickness at the subscapular and triceps (mm).
- Bilateral pedal edema (Yes, No).
- Weight-for-age z-score (WAZ) both numeric and categorical (-3 to -2, \leq -3).
- Weight-for-length z-score (WLZ).
- Birth weight (grams).
- Gestational age (weeks).
- Birth delivery method (C-Section, Vaginal birth).
- Discharge destination (Home, Nutritional Rehabilitation Unit).
- Primary type of feeding the infant has received since birth (Exclusively breastmilk, Formula exclusively, A mix of breastmilk and other types of feedings, Other milk exclusively).
- Antibiotics received within prior 30 days (Yes, No).
- Have refrigerator in house (Yes, No).

Confidential Page 26 of 50

See Section 11.5.1 for the calculation of WAZ, Section 11.6.6 for the calculation of WLZ and the derivations of baseline values of MUAC and head circumference.

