11.5.2.1 Analysis of endpoint

WAZ will be summarized using descriptive statistics for actual and CFB values by visit and treatment group.

A MMRM will be used to estimate the difference in mean CFB between Bi-26 and Placebo, adjusting for covariates baseline WAZ, age (in days), country and discharge destination. The model will use CFB in WAZ as outcome and include the following effects:

- Fixed effects: Treatment, Visit (categorical), Treatment*Visit interaction, WAZ at baseline (continuous), Age (in days) at baseline, Country, Discharge destination
- Random intercepts: participant.

and will be fit using data from all planned follow-up visits where WAZ was measured, ie, Day 28, 56, and 90 visits. The adjusted interaction effects (Treatment*Visit) will be presented as estimates of the difference in CFB between treatment groups at each follow-up visit (Day 28, 56, and 90). The associated 95% CIs and p-values will be presented. PROC MIXED will be used to fit the models. SAS code for the models is provided in Appendix 3. If the WAZ score is not normally distributed, an appropriate transformation, such as the natural log, will be used as outcome for analysis. Normality will be investigated using q-q plots.

A participant listing of WAZ will be presented with actual values and CFB.

The descriptive table, model and listing will use the mITT population. The summary table will be repeated for the PP population.

Line graphs with the means and 95% CIs for WAZ will be presented by treatment group for visits Baseline, 28, 56, and 90.

Confidential Page 32 of 50

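### The estimand tables adjust the primary and key secondary comparisons for an undefined feeding covariate, but neither model contains one and SAP Section 9 does not declare the omission

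*SAP*

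**What the plan says.** **Estimand tables.** Protocol 9.7, Table 4, gives the primary summary as "Mean change from baseline in WAZ in the Bi-26 group compared to placebo with stratification blocking factors and feeding regimen covariate(s". SAP 6.1, Table 1, repeats it: the groups are compared "with stratification blocking factors and feeding regimen covariate(s". For the key secondary endpoint, SAP 6.2, Table 2, has "Mean change from baseline in weight in the Bi-26 group compared to placebo with stratification blocking factors and feeding regimen covariate(s", matching Protocol Table 5.

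**Models.** SAP 11.5.2.1 describes the primary model as "adjusting for covariates baseline WAZ, age (in days), country and discharge destination" and lists the terms: "Fixed effects: Treatment, Visit (categorical), Treatment*Visit interaction, WAZ at baseline (continuous), Age (in days) at baseline, Country, Discharge destination", with a random intercept for participant. SAP 11.5.3.1 uses the same model for weight, with baseline weight in place of baseline WAZ.

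**Feeding elsewhere in the SAP.**
- Section 11.4.2 defines the proportion of feedings from breastmilk, taken from the diary up to the Day 56 visit.
- Section 11.5.2.4.2 makes that proportion one of several factors that may be added to a WAZ sensitivity model. It is kept if its p-value is below 0.2.
- Section 8.2 lists categories of the same proportion as a possible subgroup.
- Section 11.2 summarises a baseline variable, "Primary type of feeding the infant has received since birth", which enters no model.

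**Declared changes.** SAP Section 9 lists two: WAZ is included in the dynamic randomisation, and the populations for some secondary endpoints are changed. Neither concerns feeding.

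**The concern.** The SAP tables promise an adjustment that the SAP models do not make. The SAP therefore disagrees with itself as well as with the Protocol, and the section meant to record departures does not mention it.

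The undefined term makes this more than untidy. An analyst who tried to honour the tables would find only one feeding variable defined for modelling, the breastmilk share through Day 56. That share accumulates after randomisation. If the supplement changes appetite, tolerance or illness, it may change feeding too, and conditioning on the share could then bias the treatment contrast.

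A safer variable is already collected. Protocol 8.1 has the mother asked at screening about feeding since birth. It is a plausible predictor of weight gain, because the product's rationale is the breakdown of milk oligosaccharides. At stake are a clean pre-specification of the primary analysis and, to a lesser degree, some precision.

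**Working it through.** **1. Tables against models**

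| Endpoint | Adjustment in the estimand tables | Covariates in the model | Feeding term? |
|---|---|---|---|
| WAZ change, Day 56 (primary) | Stratification factors and feeding | Baseline WAZ, age, country, discharge destination | No |
| Weight change, Day 56 (key secondary) | Stratification factors and feeding | Baseline weight, age, country, discharge destination | No |

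The primary model carries through the first half of the phrase (WAZ and age as continuous terms, country, discharge destination) but not the second. SAP Table 8 shows the primary analysis as a plain MMRM and places the confounder-adjusted MMRM under secondary and sensitivity analyses. The secondary estimand for response over time carries the same phrase in SAP Table 2, and SAP 11.5.4.1 reuses the same model, so it has the same gap. The SAS code that the SAP places in Appendix 3 is not visible in the text available for this review and was not checked. The written term lists are explicit without it.

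**2. Effect on the treatment contrast**

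In a linear model with randomised treatment, including or leaving out a baseline covariate does not change the mean difference being estimated. It changes only the residual variance. Any cost is therefore in precision.

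**3. The plan's own sample size**

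Inputs from Protocol 9.4: difference 0.45, SD 1.3, two-sided alpha 5%, power at least 90%. The two-sample t-test solution is 176.35 per group, rounded up to 177 (354 in total), with power 90.1%. This matches the plan. The calculation uses no covariates.

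**4. What a feeding covariate could add**

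Subtracting the plan's 10% loss to follow-up and 3% mortality leaves 396 × (1 − 0.10 − 0.03) = 344.52 evaluable infants, or 172.26 per arm. Let E be the share of variance that the existing covariates explain, and F the share of the remaining variance that feeding explains. Then

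SD = 1.3 × √[(1 − E)(1 − F)]

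and power comes from the noncentral t distribution. The documents give neither E nor F, so both are assumptions.

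| Assumed E | F = 0 | F = 2% | F = 10% | Gain (points) |
|---|---|---|---|---|
| 0% | 89.3% | 89.9% | 92.2% | 0.6 to 2.9 |
| 20% | 94.8% | 95.1% | 96.5% | about 0.4 to 1.8 |
| 30% | 96.9% | 97.2% | 98.1% | about 0.3 to 1.2 |

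The row with E = 0 applies F to the unadjusted planning SD, as if baseline WAZ, age, country and discharge destination explained nothing. It is the upper end of the gain. Over the whole table the gain is roughly 0.3 to 2.9 points.

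**The case against.** The strongest reply is that the operative plan is clear. Section 11.5.2.1 lists the model term by term, Table 8 labels one analysis as primary, and no feeding-adjusted primary model appears anywhere. On this view the phrase is a leftover from the Protocol, and feeding is examined elsewhere: in the WAZ sensitivity model and as a possible subgroup for both WAZ and weight (SAP 11.5.2.2 and 11.5.3.2). Much of this stands. A reader might infer that the plan has two rival primary analyses. Table 8 does not support that.

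The second reply is that the precision argument is thin. The 2% to 10% range has no source in the documents. Inclusion criterion 9 requires some breastmilk feeding, which narrows the variation, and country may absorb part of the rest. This stands too. A reader might turn the assumed range into extra infants: 344.52/(1 − 0.02) − 344.52 is about 7, and 344.52/(1 − 0.10) − 344.52 is about 38. That arithmetic follows from the assumption, but nothing in the plan supports the assumption, so it is not a finding.

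The third reply is that feeding regimen may have meant on-study feeding, since Protocol 6.4 describes a daily diary. Moving a post-randomisation variable to a sensitivity analysis would then be sensible. That is possible, but the change would still have to be declared, and Section 9 does not declare it. None of the replies removes the contradiction between the SAP's tables and its models.

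**Conclusion.** The point holds as an undeclared inconsistency in the pre-specified primary and key secondary analyses, centred on a covariate that is never defined. It should be corrected, but it does not threaten validity.

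A reader might conclude that the planned model estimates a different estimand or gives a biased answer. The documents do not support that: treatment is randomised, the model is linear, and the target mean difference is the same with or without a baseline feeding term. Bias could arise only if someone met the tables' wording by putting the Day 56 breastmilk share into the primary model.

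The possible loss of precision is small, roughly 0.3 to 2.9 points of power. It rests on an assumed 2% to 10% of residual variance explained by feeding, an assumed 0% to 30% explained by the existing covariates, and the planning values of 0.45 and 1.3 with 344.52 evaluable infants.

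**What to change.** Make one of two changes before unblinding, which is the Protocol's own deadline for a final SAP (Protocol 9.6).

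**Preferred.** State that the feeding regimen covariate is baseline feeding type, grouped as exclusive breastmilk since birth versus mixed or other. Add it as a fixed effect in SAP 11.5.2.1 and 11.5.3.1. State that the post-randomisation breastmilk share is not to be used in the primary model. Give a rule for missing feeding type, such as a missing category, because SAP 11.2 allows for missing baseline values and PROC MIXED drops records with a missing covariate. This keeps the Protocol's commitment.

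**Alternative.** Delete the feeding phrase from SAP Tables 1 and 2 and declare the change in SAP Section 9. This also resolves the contradiction and leaves the models as they are.

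The preferred change costs one or two degrees of freedom and one missing-data rule. The alternative costs only the text edits, and forgoes whatever precision the baseline variable would have added.
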